4. LIST OF ABBREVIATIONS AND DEFINITIONS OF TERMS

The following abbreviations and specialist terms are used in this study protocol:

Abbreviation	Definition
AE	adverse event
ECG	electrocardiogram
eCRF	electronic case report form
EEG	electroencephalogram
FDA	Food and Drug Administration
GCP	Good Clinical Practice
GMP	Good Manufacturing Practice
ICF	informed consent form
ICH	International Council for Harmonisation of Technical Requirements for Pharmaceuticals for Human Use
IEC	independent ethics committee
IP	investigational product
IRB	institutional review board
IRT	interactive response technology
MDS	Movement Disorder Society
MoCA	Montreal Cognitive Assessment
MRI	magnetic resonance imaging
NMDA	N-methyl-D-aspartate
PAM	positive allosteric modulator
PD-MCI	Parkinson's disease mild cognitive impairment
QTcF	QT corrected according to Fridericia's formula
SAE	serious adverse event
SAP	statistical analysis plan
SUSAR	Suspected unexpected serious adverse reaction
TEAE	treatment-emergent adverse event
WHO	World Health Organization

5. INTRODUCTION

Mild cognitive impairment is common in patients who have Parkinson's disease, and is associated with decreased quality of life and impaired functioning. Moreover, patients with PD mild cognitive impairment (PD-MCI) are at a high risk for developing dementia (Litvan 2011). Preclinical data indicate that patients who have PD have reduced plasma levels of a specific oxysterol, 24(S)-hydroxycholesterol (24SHC; Di Natale 2018). This molecule acts as an endogenous positive allosteric modulator (PAM) of the NMDA receptor (Paul 2013) and has been correlated with performance on cognitive tasks. NMDA receptors are a subtype of glutamate receptors with a fundamental and well-documented role in regulating synaptic strength, health, and plasticity.

SAGE-718 is a novel oxysterol-based NMDA receptor PAM that acts at the 24SHC binding site and modulates the response of the receptor to endogenous glutamate. SAGE-718 only affects receptor function in the presence of endogenous glutamate – it does not directly activate the receptor and is not expected to cause NMDA receptor-associated glutamatergic excitotoxicity. Positive modulation of NMDA receptors is hypothesized to produce beneficial effects in conditions associated with reduced NMDA receptor function, activity, or expression. Preclinical studies have shown promise for improving cognitive deficits in conditions with decreased plasma levels of the endogenous NMDA receptor PAM 24SHC (Collingridge 2013).

SAGE-718 has been well tolerated in both healthy participants and a small cohort of Huntington's disease participants in previous clinical studies. However, based on nonclinical findings, the US Food and Drug Administration imposed a median maximum concentration (C_{max}) cap of 45 ng/mL. To date, clinical studies have used doses that resulted in exposures within this cap; neither SAEs nor AEs leading to discontinuation have been reported. A once-daily 3-mg dose of SAGE-718 is not predicted to exceed a median C_{max} of 45 ng/mL. For additional information on exposure caps, see the SAGE-718 Investigator's Brochure.

A direct correlation between SAGE-718 Oral Tablet exposure and fat intake has been observed in healthy adults, with significantly lower exposure in fasting participants than in the same participants after moderate and high fat-containing meals. Additionally, as fat levels increased, exposure variability decreased, allowing for more predictable C_{max} levels. Thus, in this study SAGE-718 will be administered after consumption of a morning meal containing approximately 30 g of fat. Based on the data from healthy participants, this regimen is projected to produce a median C_{max} of approximately 35 to 40 ng/mL at steady state.

The safety, tolerability, and [REDACTED] of SAGE-718 Oral Tablet will be evaluated in this open-label study in participants with a diagnosis of PD-MCI. Additional data on the effects of SAGE-718 in participants with PD-MCI will be collected throughout, including assessments of [REDACTED]

6. STUDY OBJECTIVES AND ENDPOINTS

6.1. Objectives

6.1.1. Primary Objective

The primary objective of this study is to evaluate the safety and tolerability of orally administered SAGE-718 in participants with PD-MCI.

[REDACTED]

- [REDACTED]
- [REDACTED]
- [REDACTED]
- [REDACTED]
- [REDACTED]

6.2. Endpoints

6.2.1. Primary Endpoint

The primary endpoint of this study is the incidence of treatment-emergent adverse events (TEAEs).

6.2.2. Secondary Endpoint

The secondary endpoint of this study will be assessed as the change from baseline in vital signs, clinical laboratory analytes, electrocardiograms (ECGs), and responses on the Columbia–Suicide Severity Rating Scale (C-SSRS).

[REDACTED]

- [REDACTED]
- [REDACTED]
- [REDACTED]
- [REDACTED]
- [REDACTED]
- [REDACTED]
- [REDACTED]

7. INVESTIGATIONAL PLAN

7.1. Overall Study Design

This is an open-label study evaluating the safety and tolerability of SAGE-718 and its effects on [REDACTED] in participants with PD-MCI. Eligible participants with a confirmed diagnosis of idiopathic PD by 2015 Movement Disorder Society (MDS) criteria (Berardelli 2013) at Screening and who meet MDS Task Force Criteria for MCI in PD (excluding requirement for UK PD Brain Bank diagnostic criteria) will receive a 3.0 mg dose of SAGE-718 daily for 14 days (Part A) or for 28 days (Part B). Participants will be instructed to take the daily dose of investigational product (IP) in the morning within 1 hour of initiating a meal containing approximately 30 g of fat. Assessments will be performed as outlined in the Schedules of Assessments (Table 2 and Table 4) and the [REDACTED].

In the setting of public health advisories due to COVID-19 or similar risks to patient safety, assessments scheduled to be conducted at the study site may be performed via telephone/video if feasible. For assessments that cannot be conducted by phone or video, an in-home visit may be conducted.

7.1.1. Screening Period

The Screening Period begins with the informed consent process for prospective participants, including study partners. Subsequent screening assessments will be performed between Day -21 and Day -8 to determine eligibility, including assessments of [REDACTED].

7.1.2. Baseline Period

The Baseline Period will occur from Day -7 through Day -1. During this period, each participant will receive dietary counseling to aid in choosing a morning meal containing approximately 30 g fat to consume prior to dosing. On Day -7 (± 1 day), participants will visit the clinic for confirmation of continued eligibility and collection of baseline [REDACTED] and safety data. Additionally, participants will be trained on the use of a mobile data capture device to perform daily [REDACTED]. Participants will continue to complete daily assessments of [REDACTED] using the mobile device at home during the Baseline Period. On Day -1, participants will return to the study site for confirmation of continued eligibility and collection of baseline [REDACTED] and safety data.

7.1.3. Treatment Period

Beginning on Day 1 and continuing through Day 14 in Part A and Day 28 in Part B, participants will self-administer 3.0 mg SAGE-718 (as six 0.5-mg oral tablets), once per day in the morning within 1 hour after initiating a meal containing approximately 30 g of fat, in accordance with the guidelines provided in a nutritional information brochure. Participants will continue to complete daily assessments of [REDACTED] via mobile device either remotely (at home), or in the clinic at scheduled visits and will track IP dosing and predose food intake in a participant diary.

At scheduled visits during the Treatment Period, participants will arrive at the clinic in the morning prior to IP dosing and completion of daily mobile device tasks. Following predose

procedures, participants will eat a morning meal, then take the IP and complete the mobile device tasks under staff supervision

At scheduled clinic visits during the Treatment Period, safety, efficacy, and [REDACTED] will be performed, and study staff will dispense a sufficient amount of SAGE-718 for daily administration until the next scheduled study visit. In addition to weekly clinic visits, study staff will contact participants by telephone on Day 4 to document any TEAEs and/or changes in concomitant medications.

7.1.4. Follow-up Period

In Part A, study staff will contact participants by telephone on Day 21 to document any AEs and/or changes in concomitant medications. Participants will return to the clinic on Day 28 (± 2 days) for a follow-up visit.

In Part B, participants will return to the clinic for 2 follow-up visits on Day 35 and Day 42.

7.2. Number of Participants

Up to 33 participants (11 in Part A and 22 in Part B) are planned to be dosed to obtain up to 30 participants who complete dosing in this study. Additional participants may be dosed if the early discontinuation rate is greater than 10%.

7.3. Treatment Assignment

In this open-label study, all participants will receive 3.0 mg of SAGE-718 once daily for 14 days in Part A and for 28 days in Part B.

7.4. Dose Adjustment Criteria

Dosing may be interrupted in an individual participant due to an AE considered by the investigator to be related to IP, however, no individual dose reductions will be permitted.

7.4.1. Stopping Criteria

If clinical events suspicious for seizure occur after Screening, an unscheduled electroencephalogram (EEG) will be performed for review by an independent epileptologist to identify evidence of seizure activity (see Section 12.1.6). Should the independent epileptologist identify evidence for a subclinical or clinical seizure, dosing with SAGE-718 will be stopped for that participant.

7.4.2. Dose Evaluation Committee

A Dose Evaluation Committee may be convened to review [REDACTED] and safety data when at least 5 participants have completed 14 days of dosing to consider adjusting the dose, administration schedule, or food intake recommendations for subsequent participants. The Dose Evaluation Committee will include, at a minimum, the Sage program medical lead, a Sage Drug Safety and Pharmacovigilance physician, and a clinical operations representative and will be supported by a Sage biostatistician.

7.5. Criteria for Study Termination

Sage Therapeutics may terminate this study or any portion of the study at any time for safety reasons, including the occurrence of AEs or other findings suggesting unacceptable risk to participants, or for administrative reasons. In the event of study termination, Sage Therapeutics will provide written notification to the investigator. Investigational sites must promptly notify their institutional review board (IRB)/independent ethics committee (IEC), where required, and initiate withdrawal procedures for participants.

8. SELECTION AND WITHDRAWAL OF PARTICIPANTS

8.1. Participant Inclusion Criteria

To be eligible to enroll in this study, participants must:

1. Be capable of providing informed consent
2. Have signed an informed consent form prior to any study-specific procedures being performed
3. Be willing and, in the opinion of the investigator, able to comply with study procedures
4. Be between the ages of 50 and 75 years, inclusive, at Screening
5. Meet the following criteria for PD-MCI:
 - a. Have a confirmed diagnosis of idiopathic PD according to 2015 MDS clinical diagnostic criteria
 - b. Meet MDS Task Force Criteria for MCI in PD (excluding requirement for UK PD Brain Bank diagnostic criteria)
6. Have a score of 20 to 25 (inclusive) on the MoCA at Screening
7. Meet criteria for Hoehn and Yahr Stage I to III (mild to moderate motor severity) at Screening
8. Have an estimated premorbid IQ ≥ 85 (as assessed by the Test of Premorbid Functioning [TOPF], performed at Screening)
9. Be willing to invite a study partner who is reliable, competent, and at least 18 years of age to participate in the study
10. Be ambulatory, able to travel to the study center, and in the opinion of the investigator likely to be able to continue to travel to the study center to complete study visits for the duration of the study
11. Have stable concomitant medication dose and frequency for at least 4 weeks prior to the first IP administration that is expected to remain stable for the duration of the study
12. Have stable motor symptoms for at least 4 weeks prior to screening, in the opinion of the investigator
13. Agree, if female, to use an acceptable highly effective method of contraception (as defined in Section 9.2.4) during participation in the study and for 30 days following the last dose of IP, unless she is postmenopausal (defined as no menses for 12 months without an alternative medical cause and confirmed by follicle stimulating hormone [FSH] > 40 mIU/mL), surgically sterile (hysterectomy or bilateral oophorectomy or bilateral salpingectomy), or does not engage in sexual relations which carry a risk of pregnancy
14. Agree, if male, to use an acceptable method of highly effective contraception (as defined in Section 9.2.4) during the Treatment Period and for 2 weeks after receiving the last dose of IP, unless the participant does not engage in sexual relations that carry a risk of pregnancy

15. Agree, if male, to abstain from sperm donation during the Treatment Period and for 2 weeks after receiving the last dose of IP
16. Agree to refrain from drugs of abuse and alcohol for the duration of the study

8.2. Participant Exclusion Criteria

To be eligible to enroll in this study, participants must not:

1. Have participated previously in a clinical study of SAGE-718, or have used any other investigational drug, biologic, or device or have participated in a clinical drug, biologic, or device study within 30 days or 5 half-lives (whichever is longer) prior to Screening
2. Have clinically significant comorbid medical conditions, a chronic condition that is unstable or requires more than 2 medications to be controlled, or be taking concomitant medications that, in the opinion of the investigator, may make the participant unsuitable for inclusion or have the potential to compromise safety and/or compliance with study requirements
3. Have a diagnosis of dementia of any etiology, including but not limited to: Dementia associated with PD (probable or possible), Dementia with Lewy Bodies, Alzheimer's Dementia, and Vascular Dementia
4. Have any indication of parkinsonism other than idiopathic PD, including secondary parkinsonism or atypical parkinsonism
5. In the opinion of the investigator, be experiencing unpredictable fluctuations in motor and/or nonmotor symptoms associated with PD
6. Have an ongoing central nervous system condition other than idiopathic PD, including active neurologic and/or nonremitted psychiatric disorders, in the opinion of the investigator
7. Have a history of brain surgery, deep brain stimulation, a significant head injury causing loss of consciousness greater than 30 minutes, or hospitalization due to a brain injury
8. Have a history, presence, and/or current evidence of intracranial abnormality (eg, stroke, hemorrhage, space-occupying lesion)
9. Have experienced significant psychotic symptoms within the past 3 months, including those associated with PD medications, as determined by the investigator
10. Have a history of possible or probable cerebral amyloid angiopathy according to the Boston Criteria ([Greenberg 1995](#))
11. Be receiving any of the following prohibited medications:
 - a. Medications with potent effects at the N-methyl-D-aspartate (NMDA) receptor, including memantine, amantadine, ketamine, or related compounds
 - b. Medications that inhibit cholesterol absorption (eg, ezetimibe)
 - c. Bile acid sequestrants (eg, colestevlam, cholestyramine)
 - d. Other medications given at doses, frequencies, or in combinations that are likely, in the opinion of the investigator, to have a deleterious effect on cognitive performance, based on the 2019 American Geriatrics Society Updated Beers[®] Criteria for

Potentially Inappropriate Medication Use in Older Adults ([American Geriatrics Society 2019](#))

- e. Prescribed cannabis or other THC-containing substances
12. Have an alcohol or drug use disorder within the past 12 months as per DSM-5 criteria
 13. Have a history of seizures or epilepsy, with the exception of a single episode of febrile seizures in childhood
 14. Have current or recent suicidality, defined as follows:
 - a. Suicidal ideation within the past month, as evidenced by a score of 4 (active suicidal ideation with some intent to act, without specific plan) or 5 (active suicidal ideation with specific plan and intent) on the screening or baseline Columbia–Suicide Severity Rating Scale (C-SSRS)
 - b. Suicidal behavior within the past year, as evidenced by a "Yes" on any of the 5 C-SSRS Suicidal Behavior Items (actual attempt, interrupted attempt, aborted attempt, preparatory acts, or behavior) on the C-SSRS during Screening or Baseline
 - c. Participant presents a serious risk of suicide in the opinion of the investigator.
 15. Have any of the following clinically significant medical conditions:
 - a. Any clinically significant finding on 12-lead ECG during Screening or Baseline
 - b. Supine vital signs outside of the following ranges during Screening or Baseline; vital sign measurements may be repeated once if initial values exceed these ranges:
 - Heart rate <50 or >100 bpm
 - Systolic blood pressure <100 or >160 mmHg
 - Diastolic blood pressure <60 or >100 mmHg
 16. Have significant hepatic, renal, cardiovascular, pulmonary, gastrointestinal, hematological, immunologic, ophthalmologic, metabolic, or oncological disease
 17. Have a history, presence, and/or current evidence of serologic positive results for HIV-1 or HIV-2
 18. Have a positive pregnancy test or be lactating at Screening or Day -1
 19. Be investigative site personnel, sponsor personnel, or an immediate member of their family (spouse, parent, child, or sibling whether biological or legally adopted)

8.3. Screen Failures

Screen failures are defined as participants who consent to participate in the clinical study but are not subsequently assigned to study intervention or are not entered in the study. A minimal set of screen failure information will be collected, including demography, screen failure details, eligibility criteria, and any SAEs.

Individuals who do not meet the criteria for participation in this study (screen failure) may be rescreened once, with the approval of the medical monitor. Rescreened participants will be assigned a new participant number.

8.4. Investigational Product Discontinuation and Early Termination from the Study

A participant may withdraw from the study at any time at his/her own request for any reason. The investigator may discontinue a participant from the study and/or from IP for safety, behavioral, compliance, or administrative reasons.

The reason for IP discontinuation and/or the reason for early termination from the study must be documented in the participant's study record and recorded in the participant's electronic case report form (eCRF).

The investigator must notify the sponsor and/or the medical monitor when a participant stops participation in the study for any reason.

8.4.1. Investigational Product Discontinuation

Participants who discontinue IP will be invited by the investigator to complete all of the scheduled study visits and assessments through the end of the Treatment Period. Those who decline to continue participation will be asked to complete an Early Termination Visit.

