2. SYNOPSIS

Name of Sponsor/Company: Sage Therapeutics, referred to herein as “Sage”
Name of Investigational Product: SAGE-718 Oral Tablet
Name of Active Ingredient: SAGE-718
Title of Study: An Open-Label Evaluation of the Safety and Tolerability of SAGE-718 in Participants with Parkinson’s Disease Mild Cognitive Impairment
Number of Sites and Study Location: Approximately 10 sites in the US
Phase of Development: 2
Planned Duration for each Study Participant: Each participant’s involvement will last approximately 7 weeks in Part A and 9 weeks in Part B, including a maximum 2-week Screening Period, a 1-week Baseline Period, a 2-week Treatment Period in Part A or 4-week Treatment Period in Part B, and a 2-week Follow-up Period.
Objectives: Primary Objective 
To evaluate the safety and tolerability of orally administered SAGE-718 in participants with Parkinson’s disease mild cognitive impairment (PD-MCI) 
[REDACTED]

Endpoints: Primary Endpoint 
Incidence of treatment-emergent adverse events (TEAEs) Secondary Endpoint 
Change from baseline in vital signs, clinical laboratory analytes, electrocardiograms (ECGs), and responses on the Columbia–Suicide Severity Rating Scale (C-SSRS) 
[REDACTED]

[REDACTED]

Study Description:

This is an open-label study evaluating the safety and tolerability of SAGE-718 and its effects on [REDACTED] in participants with PD-MCI. Eligible participants with a confirmed diagnosis of idiopathic PD by 2015 Movement Disorder Society (MDS) criteria (Berardelli 2013) at Screening and who meet MDS Task Force Criteria for MCI in PD (excluding requirement for UK PD Brain Bank diagnostic criteria) will receive a 3.0 mg dose of SAGE-718 daily for 14 days (Part A) or for 28 days (Part B). Participants will be instructed to take the daily dose of investigational product (IP) in the morning within 1 hour of initiating a meal containing approximately 30 g of fat. Assessments will be performed as outlined in the Schedules of Assessments (Table 2 and Table 4) and the [REDACTED]

In the setting of public health advisories due to COVID-19 or similar risks to patient safety, assessments scheduled to be conducted at the study site may be performed via telephone/video if feasible. For assessments that cannot be conducted by phone or video, an in-home visit may be conducted.

Screening Period

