8.4.2. Early Termination from the Study

For participants who are terminated from the study early, if possible, an Early Termination Visit should be conducted as described in [Table 2](#) or [Table 4](#). The participant will be permanently discontinued both from the IP and from the study at that time.

If the participant withdraws consent for disclosure of future information, the sponsor will retain and continue to use any data collected before such a withdrawal of consent.

If a participant withdraws from the study, he/she may request destruction of any samples taken and not tested, and the investigator must document this in the site study records.

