12.2. Adverse Events and Serious Adverse Events

12.2.1. Adverse Event Definition

An AE is any untoward medical occurrence in a patient or clinical investigation participant administered a pharmaceutical product and that does not necessarily have a causal relationship with this treatment. An AE can therefore be any unfavorable and unintended sign (including an abnormal laboratory finding), symptom or disease temporally associated with the use of a medicinal (investigational) product whether or not related to the medicinal (investigational) product. In clinical studies, an AE can include an undesirable medical condition occurring at any time, including baseline or washout periods, even if no study treatment has been administered.

A TEAE is defined as an AE with onset after the start of IP, or any worsening of a preexisting medical condition/AE with onset after the start of IP and throughout the study. The term IP includes any Sage IP, a comparator, or a placebo administered in a clinical study.

Laboratory abnormalities and changes from baseline in vital signs, and ECGs are considered AEs if they result in discontinuation or interruption of study treatment, require therapeutic medical intervention, meet protocol specific criteria (if applicable) or if the investigator considers them to be clinically significant. Any abnormalities that meet the criteria for a SAE should be reported in an expedited manner. Laboratory abnormalities and changes from baseline in vital signs and ECGs that are clearly attributable to another AE do not require discrete reporting (eg, electrolyte disturbances in the context of dehydration, chemistry, and hematologic disturbances in the context of sepsis).

All AEs that occur after any participant has signed the informed consent form (ICF) and throughout the duration of the study, whether or not they are related to the study, must be reported to Sage Therapeutics.

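### Sections 8.4.1 and 8.4.2 leave the Follow-up Period out for participants who stop SAGE-718 early, so many of them would have less recorded off-drug adverse event observation than completers

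*Protocol*

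**What the plan says.** Dosing is planned "Beginning on Day 1 and continuing through Day 14 in Part A and Day 28 in Part B" (Protocol Section 7.1.3). The synopsis gives each participant "a 2-week Treatment Period in Part A or 4-week Treatment Period in Part B, and a 2-week Follow-up Period". Section 7.1.4 fills in the follow-up. Part A has a telephone call on Day 21, and then "Participants will return to the clinic on Day 28 (± 2 days) for a follow-up visit". For the other part: "In Part B, participants will return to the clinic for 2 follow-up visits on Day 35 and Day 42". Neither sentence is restricted to people who finished dosing.

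Section 8.4.1 deals with people who stop the investigational product (IP). They are invited to "complete all of the scheduled study visits and assessments through the end of the Treatment Period", and the Follow-up Period is not mentioned. "Those who decline to continue participation will be asked to complete an Early Termination Visit". On early termination, Section 8.4.2 says: "The participant will be permanently discontinued both from the IP and from the study at that time". No later contact is stated.

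The primary endpoint is the incidence of treatment-emergent adverse events (TEAEs). Under Section 12.2.1 these are AEs that begin after IP starts, and "any worsening of a preexisting medical condition/AE with onset after the start of IP and throughout the study". No cut-off is set at a fixed time after the last dose.

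**The concern.** With no post-dose cut-off, the time during which a TEAE can be recorded ends when the participant's study participation ends. Section 7.1.4 read alone gives everyone the Follow-up Period. Section 8.4.1 read alone gives a person who stopped IP an earlier end point, and a site has to choose between them. If sites follow 8.4.1 and 8.4.2, some people who stopped would be observed off drug for less time than those who finished.

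What could be lost is new late-onset information: additional preferred terms, a higher maximum severity, serious adverse events (SAEs) not judged related to IP, or a first TEAE in someone who stopped for another reason. The follow-up vital signs, ECG, laboratory and C-SSRS assessments, which feed the secondary endpoint, would be lost too. The shortfall would not show in the results. SAP Section 16.1 reports numbers and percentages of participants, Section 13.9.1 summarises exposure duration, and no visible output in SAP Appendix-G gives time from last dose to last AE assessment.

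**Working it through.** **Inputs.** Last planned dose: Day 14 (A), Day 28 (B), Section 7.1.3. Final follow-up visit: Day 28 (A), Day 42 (B), Section 7.1.4. Planned numbers: 11 in A and 22 in B, 33 in total, for 30 completers at 10% dropout, Sections 7.2 and 13.8.

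**The plan's own figures.** Completer off-drug time is final follow-up day minus last dose day: 28 − 14 = 14 days (A) and 42 − 28 = 14 days (B), the stated 2 weeks. Total participation is 2 + 1 + 2 + 2 = 7 weeks (A) and 2 + 1 + 4 + 2 = 9 weeks (B), also as stated.

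**Early stoppers under Section 8.4.1.** Let d be the day of the last dose. If the participant stays to the end of the Treatment Period, off-drug time is 14 − d in Part A and 28 − d in Part B.

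| Group | Last dose day d | Off-drug days | Against 14 for a completer |
|---|---|---|---|
| Part A, stays to Day 14 | 1 to 13 | 13 down to 1 | shorter in all 13 cases |
| Part B, stays to Day 28 | 1 to 13 | 27 down to 15 | longer |
| Part B, stays to Day 28 | 14 | 14 | equal |
| Part B, stays to Day 28 | 15 to 27 | 13 down to 1 | shorter |
| Either part, leaves at ET visit | any | time from last dose to ET visit | shorter if under 14 days |

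The documents do not fix the timing of the ET visit; if it is held promptly, the last row is close to 0 days.

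**Visit windows.** The final visit may fall 2 days either side of its target (for Part B, see SAP Section 10.1), so a completer has 12 to 16 off-drug days. Against 12 days, Part A stoppers are still shorter for d = 3 to 13, equal at d = 2 (12 days) and longer at d = 1 (13 days). The Part B break-even moves from d = 14 to d = 16 (28 − 16 = 12) or d = 12 (28 − 12 = 16).

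**How many people.** 30 / (1 − 0.10) = 33.3, consistent with the stated figure of approximately 33. Then 33 × 0.10 = 3.3, or about 3 participants: 11 × 0.10 = 1.1 in A and 22 × 0.10 = 2.2 in B. Not all of the Part B group would be short of 14 days.

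**If the Follow-up Period also applied.** Off-drug time for those who remain becomes 28 − d in A (15 to 27 days for d = 13 to 1) and 42 − d in B (15 to 41 days for d = 27 to 1). That is never below a completer's 14 days.

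**The case against.** Section 8.4.1 is an invitation and is silent on the follow-up visits; it does not forbid them. Section 7.1.4 can be read as covering everyone. That is fair, and it is why this is a matter of reconciling sections. Naming an earlier end point still gives sites reason to stop there.

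Section 12.2.1 already requires that people who stop IP because of an AE be followed until it resolves, stabilises or ceases to matter clinically, whatever the cause. This protects the known event. It does not look for new ones.

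Two other limits might seem to prove selective loss: unresolved AEs are followed after the last assessment without eCRF entry (Section 12.2.1), and SAEs after the follow-up time are reported only if judged related (Section 12.2.5). Both apply equally to completers, so neither shows selective loss.

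A reader might infer that TEAE incidence is biased downward, mainly in people who stopped for tolerability. The documents do not support this. SAP Section 16.1 counts participants with at least one TEAE, and once within each system organ class and preferred term. Someone who stopped because of a TEAE is therefore already in the overall numerator. The 10% is all-cause dropout, and Section 5 says that no AE leading to discontinuation had been reported in clinical studies to date. There is also no comparator, so no between-group contrast is distorted.

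**Conclusion.** The point holds, with limits. Read literally, recorded off-drug AE observation is shorter than a completer's nominal 14 days for all Part A early stoppers who stay to Day 14 (1 to 13 days), for Part B participants with a last dose on Day 15 to 27 who stay to Day 28 (1 to 13 days), and for anyone whose ET visit comes less than 14 days after the last dose. It would be wrong to conclude that everyone who stops is observed for less time: Part B participants who stop by Day 14 and stay to Day 28 have 14 to 27 days.

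About 3 of 33 participants are involved at the assumed dropout, more if dropout is higher. Overall TEAE incidence is unaffected for anyone already counted. The visible text gives no half-life and no AE onset rates, so the number of missed events cannot be computed. The result assumes nominal visit days and that sites apply 8.4.1 and 8.4.2 as written. This is a cheap improvement to safety data collection in a study whose primary objective is safety; it does not threaten the study's validity.

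**What to change.** - **Protocol.** Reconcile Sections 8.4.1 and 8.4.2 with 7.1.4, so that participants who stop IP but remain in the study are also invited to the Follow-up Period safety assessments already scheduled (Part A: Day 21 call and Day 28 visit; Part B: Day 35 and Day 42 visits). State whether any AE contact applies after an ET visit. This concerns data collection only and changes no treatment rule.
- **SAP.** List days from last dose to last AE assessment by completion status. Calendar-based follow-up will give early stoppers more than 14 days, and the listing makes that visible as well.
- **While editing.** The note to Protocol Table 4 (Part B) asks for the Day 14 assessments at early termination, whereas the matching note in SAP Appendix-B says Day 28. These should be reconciled too.

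A post-ET contact cannot simply borrow an existing call. Part B's only scheduled safety call is on Day 4, during treatment, so a later call would be new. Part A's Day 21 call is tied to the calendar: after a last dose on Day 10 it gives 21 − 10 = 11 days.

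The cost is about two protocol sentences, one listing column, and a few extra visits or calls for about 3 participants, some of whom will decline.
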